8.2 Randomization

NSCLC second-line cohort

Qualified subjects will be randomized at a 1:1 ratio to receive either 500 or 1200 mg/infusion MSB0011359C using permuted block randomization. Randomization will not be stratified. Randomization will occur upon completion of the Screening procedures and determination of subject eligibility as described in Section 6.3.

Not applicable for subjects not included in the NSCLC second-line cohort.

8.3 Endpoints

8.3.1 Primary Endpoints

The primary endpoints for the dose-escalation part of the trial are the:

- Number, severity, and duration of TEAEs according to the NCI-CTCAE v4.03
- Number, severity and duration of treatment-related AEs for all dose groups / indications according to CTCAE v4.03
- Occurrence of DLTs during the first 3 weeks (21 days) of treatment in the dose-escalation part of the trial

Except for the glioblastoma cohort, the primary efficacy endpoint for the dose-expansion part of the trial is the confirmed BOR according to RECIST 1.1 as adjudicated by the IRC (Section 2.2.2) and will be evaluated by confirmed ORR. For glioblastoma, the primary endpoint will be disease control according to RANO as adjudicated by the IRC.

8.3.2 Secondary Endpoints

The secondary endpoints for the dose-escalation part of the trial are the:

- MSB0011359C PK profile (for dose escalation), including AUC, C_{max} , C_{min} , and $t_{1/2}$
- Serum titers of antiMSB0011359C antibodies
- BOR according to RECIST 1.1 per Investigator assessment

The secondary endpoints for the expansion part of the trial are the:

- MSB0011359C PK profile (for dose escalation), including AUC, C_{max} , C_{min} , and $t_{1/2}$
- Serum titers of antiMSB0011359C antibodies

CCI
I
I
I
I

CCI
I

CCI
I

CCI
I

I

I

I

I

8.3.4 Safety Endpoints

Besides the endpoints specified as primary and secondary variables the following endpoints will be evaluated:

- Laboratory parameters

- Eye signs and symptoms
- Vital signs
- ECG parameters.

8.4 Analysis Sets

The following analysis sets will be defined separately for the dose-escalation part and the expansion cohorts in this trial, as applicable:

- **DLT Analysis Set (dose-escalation part):** All subjects with data used for implementing the dose-escalation schedule. These subjects will have received all study treatment administrations in the DLT evaluation period or should have stopped treatment because of DLTs in the DLT evaluation period.
- **Safety Analysis Set:** All subjects who receive at least 1 dose of trial treatment.
- **Full Analysis Set:** All subjects who receive at least 1 dose of trial treatment. For the NSCLC second-line cohort, the Full Analysis Set includes all subjects randomized.
- **PK Analysis Set:** All subjects who complete at least 1 infusion of IMP, and who provide at least 1 sample with a measurable concentration of MSB0011359C.
- **Immunogenicity Analysis Set:** All subjects who complete at least 1 infusion of IMP, and who have provided the blood sample prior to any MSB0011359C treatment and at least one post-treatment serum sample.

- **CCI** [REDACTED]

8.5 Description of Statistical Analyses

Full details of the planned analyses will be described in the trial Statistical Analysis Plan (SAP), separately for the dose-escalation and the expansion part of the trial.

8.5.1 General Considerations

All data recorded during the study will be presented in individual data listings performed on the Safety Analysis Set. All data will be evaluated as observed, and no imputation method for missing values will be used unless otherwise specified in the SAP. All data will be presented in a descriptive manner. Each cohort will be analyzed separately, and no multiplicity adjustment across cohorts will be performed.

Descriptive statistics will be used to summarize the trial results, that is, statistics for continuous variables may include means, medians, ranges, and appropriate measures of variability. Qualitative variables will be summarized by counts and percentages. The uncertainty of estimates will be assessed by confidence intervals. Unless otherwise specified, the calculation of proportions will be based on the sample size of the analysis set of interest. Counts of missing observations will be included in the denominator and presented as a separate category if not otherwise specified in the SAP.

The DLT Analysis Set is the underlying data set for the MTD determination. Safety analyses will be performed on the Safety Analysis Set. Baseline summaries and efficacy analyses will be performed on the Full Analysis Set. Analyses of PK variables will be performed on the PK Analysis Set. Analysis of serum titers of Anti-MSB0011359C Antibodies (ADA) will be performed on the Immunogenicity Analysis Set. CCI

The estimation of PK parameters will be performed using WinNonlin[®] Version 5.0 or higher. All other statistical analyses will be performed using SAS[®] Version 9.1.3 or higher, or R, Version 2.10.1 or higher.

Unless otherwise specified, the endpoint analyses described in the following will be performed separately for both the dose-escalation part and the expansion part of the trial.

8.5.2 Analysis of Primary Endpoints

8.5.2.1 Maximum-Tolerated Dose Determination

For determination of the MTD, individual subject data from the dose-escalation part will be reported.

In addition, for the final statistical analysis, the following will be analyzed:

- At each dose level, the number and proportion of subjects in the DLT Analysis Set who experience a DLT during the DLT evaluation period.
- At each dose level, the number and proportion of TEAEs experienced by subjects in the DLT Analysis Set during the DLT evaluation period.

The MTD will be determined according to the dose-escalation plan described in Section 5.1.3.2. The MTD is defined as the highest dose level at which no more than 1 subject out of 6 subjects treated in a cohort and evaluable for DLT determination experiences a DLT.

8.5.2.2 Best Overall Response

Except for the glioblastoma cohort, the primary efficacy endpoint for the dose-expansion part of the study is the confirmed BOR according to RECIST 1.1 as adjudicated by the IRC and will be evaluated by the confirmed ORR. For glioblastoma, the primary endpoint will be disease control according to RANO as adjudicated by the IRC.

Except for the glioblastoma cohort, the primary efficacy parameter in the expansion part is the BOR according to RECIST 1.1 as adjudicated by the IRC (Section 2.2.2) and will be evaluated by confirmed ORR. For glioblastoma, the primary efficacy parameter will be disease control according to RANO as adjudicated by the IRC.

The primary analysis of the BOR will be conducted in the Full Analysis Set. The number and proportion of BOR (defined as CR + PR) will be tabulated. For the glioblastoma cohort, the proportion of BOR of CR, PR, or SD ≥ 12 weeks according to RANO will be tabulated. The 2-sided 95% Clopper-Pearson CI will be constructed.

For a BOR of PR or CR, confirmation of the response according to RECIST 1.1 (Eisenhauer 2009) or RANO for subjects with glioblastoma (Wen 2010) will be required for the final analysis. The interim analysis will be based on unconfirmed response. The response at each scheduled tumor assessment and the BOR will be listed for each subject. The ORR, defined as the proportion of subjects with BOR of PR or CR, will be tabulated for each cohort.

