With 60 subjects treated (30 subjects from the HCC 1200 mg flat-dose ascending-dose cohort and 30 subjects from the HCC second-line or sorafenib-intolerant cohort), the study has approximately 88% power to rule out a $\leq 20\%$ ORR (null hypothesis) when the true ORR is 35% with 1-sided 0.1 alpha.

NSCLC, anti-PD-1 / anti-PD-L1 failure cohort: 80 subjects will be enrolled to characterize the tolerability, safety profile, and for preliminary evaluation of antitumor activity for previously anti-PD-1 / anti-PD-L1 treated subjects. With 80 enrolled subjects, the study has 92% power to rule out a 5% ORR when the true ORR is 15% with 1-sided 0.05 alpha.

There will be one planned interim analyses for internal planning purposes. There is no multiplicity adjustment is applied to the interim analysis. The interim analysis will occur when the first 40 subjects are evaluable for response assessment at 12 weeks (that is, have either completed the second tumor reassessment at Week 12 or discontinued the study before Week 12).

Melanoma, anti-PD-1 / anti-PD-L1 failure cohort: 30 subjects will be enrolled to characterize the tolerability, safety profile, and for preliminary evaluation of antitumor activity for previously anti-PD-1 / anti-PD-L1 treated subjects. With 30 subjects who were treated with prior anti-PD-1 / anti-PD-L1 therapy, the study has 87% power to rule out a 5% ORR when the true ORR is 20% with 1-sided 0.1 alpha.

There will be one planned interim analysis for internal planning purposes. There is no multiplicity adjustment applied to the interim analysis. The interim analysis will occur when the 30 subjects are evaluable for response assessment at 12 weeks (that is, have either completed the second tumor reassessment at Week 12 or discontinued the study before Week 12).

NSCLC, second-line cohort: Up to 80 subjects will be enrolled (randomized in a 1:1 ratio to receive either 500 or 1200 mg/infusion) to characterize the tolerability, safety profile, for preliminary evaluation of antitumor activity, and to support the overall PK data to characterize the exposure-response relationship. With 30 subjects who received 1200 mg/infusion were treated with prior platinum-based therapy, the study has 82% power to rule out a $\leq 20\%$ ORR when the true ORR is 40% with 1-sided 0.1 alpha.

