With 30 subjects treated, the study has approximately 87% power to rule out a $\leq 15\%$ ORR (null hypothesis) when the true ORR is 35% at the 10% type I error rate (1-sided).

The total sample size for the study (dose escalation and dose expansion) is expected to be up to approximately 642 subjects.

Statistics for continuous variables may include means, medians, ranges, and appropriate measures of variability. Qualitative variables will be summarized by counts and percentages. The uncertainty of estimates will be assessed by confidence intervals. The results of the safety evaluations will be tabulated and displayed by dose level / expansion cohort. Only exploratory statistical analysis will be performed. Descriptive statistics will be examined for indications of dose-related toxicity.

Listings will be produced upon completion of each dose-escalation cohort of subjects and the decision as to whether to proceed with dose-escalation, dose-reduction or to enroll another cohort at the same dose level will be determined by reviewing these data. Full details of the planned analyses will be described in the trial Statistical Analysis Plan, separately for the dose-escalation part and the expansion part.

Schedule of Assessments

Table 1 Schedule of Assessments – Dose Escalation Phase

Measure	Screening Assessments	Treatment Phase (-3 / +1 days) ^a											EoT Visit	Safety Follow-up		Long-term Follow-up ^{b,c}	
	Day -28 to First Treatment	V1	V2	V3	V4	V5	V6	V7	V7	V8	V9	V10	Until Progression	On the Day of or Within 7 Days of Decision to Discontinue ^d	28 Days (± 5 days) after Last Treatment ^e	10 Weeks (± 2 weeks) after Last Treatment	Every 12 Weeks (± 2 weeks)
		W1	W1	W2	W3	W4	W5	W7	W7	W9	W11	W13					
Written informed consent	X																
Inclusion / exclusion criteria	X	X															
Medical history	X																
Cancer disease history	X																
Prior anticancer drug / radiotherapy / procedures	X																
Other prior medications	X																
Demographic data	X																
HBV and HCV testing	X																
Ophthalmology examination including slit lamp evaluation inclusive of the anterior segment and with visual acuity ^f	X																
Physical examination ^f	X	X	X	X	X	X	X	X		X	X	X	6-weekly	X	X	X	
Dermatological assessment ^g	X				X		X	X		X	X	X	6-weekly	X	X	X	
12 lead ECG ^h	X	X/X ^h	X	X	X/X ^h		X/X ^h	X				X	6-weekly normal ECGs	X	X		

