8.1.2 Expansion Cohorts

CCI

[Redacted content]

Table 12 **The 95% Exact (Clopper-Pearson) Confidence Intervals for ORR Based on 30 Enrolled Subjects**

ORR	95% Exact Confidence Interval
0.20	(0.077, 0.386)
0.30	(0.147, 0.494)
0.40	(0.227, 0.594)
0.50	(0.313, 0.687)
0.60	(0.406, 0.773)
0.70	(0.506, 0.853)

HCC ascending-dose cohort

In order to further assess the tolerability and safety of MSB0011359C in subjects with HCC, up to 36 subjects may be enrolled in the ascending dose part of the HCC cohort. Six subjects will be enrolled at 3 mg/kg once the 3 mg/kg dose level in the dose escalation part of the trial has been cleared by the SMC. Thirty subjects will be enrolled at a 1200 mg flat dose once the 20 mg/kg dose level in the dose escalation part of the trial has been cleared by the SMC.

HCC second-line or sorafenib-intolerant cohort

Up to 70 subjects will be enrolled in the HCC second-line or sorafenib-intolerant cohort at the dose selected by the SMC during the dose-escalation part of the trial, for the purpose of assessing efficacy based on the BOR. An initial enrollment of 30 subjects will accrue if > 6 of 30 subjects in the HCC 1200 mg flat-dose ascending-dose cohort have a response (that is an ORR of at least 20%). The primary analysis will be 24 weeks after the 60th subject started treatment. The analysis will include the 30 subjects from the HCC 1200 mg flat-dose ascending-dose cohort and 30 subjects from the HCC second-line or sorafenib-intolerant cohort (assumes a similar target population as per the inclusion criteria). An additional 40 subjects may subsequently be enrolled in order to gather additional safety data.

With 60 subjects treated (30 subjects from the HCC 1200 mg flat-dose ascending-dose cohort and 30 subjects from the HCC second-line or sorafenib-intolerant cohort), the study has approximately 88% power to rule out a $\leq 20\%$ ORR (null hypothesis) when the true ORR is 35% at the 10% type I error rate (1-sided).

NSCLC anti-PD-1 / anti-PD-L1 failure cohort

With 80 subjects treated, the study has approximately 92% and 99% power to rule out a $\leq 5\%$ ORR (null hypothesis) when the true ORR is 15% and 20%, respectively, at the 5% type I error rate (1-sided).

Melanoma anti-PD-1 / anti-PD-L1 failure cohort

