The goal of this cohort is an exploration of anti-PD-L1 retreatment and initial clinical responses as a way to show confidence in the proof-of-mechanism of the addition of TGF β inhibition to the anti-PD-L1 mechanism. With 30 subjects who were treated with prior anti-PD-1 / anti-PD-L1 therapy, the study has 87% power to rule out a 5% ORR when the true ORR is 20% with 1-sided 0.1 alpha.

NSCLC second-line cohort

With 30 second-line subjects treated at 1200 mg/infusion, the study has approximately 82% power to rule out a $\leq 20\%$ ORR (null hypothesis) when the true ORR is 40% at the 10% type I error rate (1-sided).

An interim analysis will occur when the 30 subjects are evaluable for response assessment at 12 weeks (that is, have either completed the second tumor reassessment at Week 12 or discontinued the study before Week 12). If ≤ 4 responders are observed at the interim analysis, no further subjects will be enrolled into the NSCLC second-line cohort.

Pancreatic adenocarcinoma, CRC, and cervical cancer cohorts

With 30 subjects treated, the study has approximately 79% power to rule out a $\leq 10\%$ ORR (null hypothesis) when the true ORR is 25% at the 10% type I error rate (1-sided).

Ovarian cancer, TNBC, and esophageal adenocarcinoma cohorts

With 30 subjects treated, the study has approximately 87% power to rule out a $\leq 15\%$ ORR (null hypothesis) when the true ORR is 35% at the 10% type I error rate (1-sided).

Glioblastoma cohort

With 30 subjects treated, the study has approximately 97% power to rule out a $\leq 50\%$ DCR (null hypothesis) when the true DCR is 80% at the 5% type I error rate (1-sided).

SCCHN cohort

With 30 subjects treated, the study has approximately 87% power to rule out a $\leq 15\%$ ORR (null hypothesis) when the true ORR is 35% at the 10% type I error rate (1-sided).

All expansion cohorts

Except for the glioblastoma cohort, the primary efficacy endpoint for the dose expansion-part of the trial is the confirmed BOR according to RECIST 1.1 as adjudicated by the Independent Endpoint Review Committee (IRC) and will be evaluated by confirmed ORR. For glioblastoma, the primary endpoint will be disease control.

For each cohort separately (except for the HCC cohort), upon continuation of the cohort up to the targeted sample size, the primary analysis will occur 24 weeks after the start of treatment in the

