8.6 Interim and Additional Planned Analyses

Enrollment of expansion cohorts will not be stopped for the purpose of conducting their respective interim analyses but will stop if futility is met as specified.

Dose Escalation Part

In the dose-escalation part, the trial data will be evaluated before decision is made to go to the next dose level or to start with treatment in the expansion part.

Expansion Part

For all expansion cohorts except glioblastoma cohort, the endpoints in these interim analyses are ORR (confirmation is not required). For glioblastoma, the endpoint in the interim analysis will be DCR. There is no multiplicity adjustment is applied to the interim analyses. The decision rules at the interim analyses serve as guidance and are non-binding. In the absence of a control arm, outcomes in this single arm study have to be interpreted with caution, both at interim and final analyses.

CCI

HCC ascending-dose cohort

An interim analysis will be conducted 12 weeks after the final subject in the ascending-dose portion received their first dose.

If ≤ 6 responses are observed in the 30 subjects at the interim analysis, the enrollment into HCC second-line or sorafenib-intolerant cohort will be stopped. This decision criterion has 39% probability of rejecting the null hypothesis if the true response rate is 20% and 6% probability of rejecting the alternative hypothesis if the true response rate is 35%.

Enrollment of HCC second-line or sorafenib-intolerant cohort will not be stopped for the purpose of conducting this interim analysis but will stop if futility is met as specified.

HCC second-line or sorafenib-intolerant cohort

No interim analysis is planned.

NSCLC anti-PD-1 / anti-PD-L1 failure cohort

One interim analysis is planned for this cohort 12 weeks after the 40th subject in this cohort started treatment.

- If ≤ 2 responses are observed in the 40 subjects at the interim analysis, the enrollment will be stopped. This decision criterion has 32% probability of rejecting null hypothesis if the true response rate is 5% and 5% probability of rejecting alternative hypothesis if the true response rate is 15%.
- If 3 to 4 responses are observed at the interim analysis, the enrollment will be temporarily stopped until the first 40 subjects have completed tumor assessment at Week 24. After a review of the totality of data, including duration of response, DCR, and safety, the Sponsor will make a decision as to whether to resume the accrual.

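### Does a two-sided 95% interval for the primary endpoint conflict with expansion-cohort powers stated at one-sided 10% or 5%?

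*Protocol*

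**What the plan says.** Section 8.1.2 of the protocol justifies the expansion cohorts by power against a null rate. For HCC with 60 subjects, "the study has approximately 88% power to rule out a" 20% ORR when the true rate is 35%, at one-sided 10%. For pancreatic, CRC and cervical cancer with 30 subjects each, "the study has approximately 79% power to rule out a" 10% ORR when the true rate is 25%, also at one-sided 10%. The synopsis puts NSCLC second line this way: "With 30 subjects who received 1200 mg/infusion were treated with prior platinum-based therapy, the study has 82% power to rule out a" 20% ORR when the truth is 40%. NSCLC anti-PD-1/PD-L1 failure and glioblastoma use one-sided 5%.

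Section 8.5.2.2, on the primary endpoint, calls for the number and proportion of responders (disease control for glioblastoma) and adds that a "2-sided 95% Clopper-Pearson CI will be constructed". The readable text gives no test, p-value or responder cutoff for the final analysis.

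The status of these analyses is stated in three places. Section 8.5.1: "All data will be presented in a descriptive manner", with confidence intervals there to express the uncertainty of estimates. Synopsis, Statistical methods: "Only exploratory statistical analysis will be performed". Section 8.6: "outcomes in this single arm study have to be interpreted with caution, both at interim and final analyses". Section 8.5 defers full detail to the SAP. Section 6 of the supplied SAP says that plans for the interim and primary analyses by cohort were developed separately.

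**The concern.** A design that sets a null rate, an alpha and a power normally leads the reader to expect a final analysis that answers the same question at the same alpha. Here the only inferential output in the readable primary analysis is an interval whose lower limit works at one-sided 2.5%, a quarter of the design alpha in ten cohorts and half of it in the other two.

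The protocol's own Table 12 shows the effect. At 6/30 the 95% interval starts at 0.077, below the 10% null, although the design test gives p = 0.073 and rejects at 10%. At 9/30 it starts at 0.147, below the 15% null, although the test gives p = 0.028. A reader who used the printed interval as the test would say the null was not excluded when the design's own test says it was. If that reading were the plan's rule, the quoted powers would not describe the analysis performed.

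**Working it through.** **Inputs.** Cohort size n, null p0, alternative p1 and one-sided alpha come from the synopsis (Statistical methods) and Section 8.1.2. The interval comes from Section 8.5.2.2.

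**Step 1: reproduce the stated powers.** The design cutoff c is the smallest count with P(X ≥ c | n, p0) ≤ alpha, and power is P(X ≥ c | n, p1). For pancreatic, CRC and cervical (n = 30, p0 = 0.10, alpha = 0.10), P(X ≥ 5) = 0.1755 is too large and P(X ≥ 6) = 0.0732 is acceptable, so c = 6. P(X ≥ 6 | 0.25) = 0.797, against a stated 79%.

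**Step 2: find where the 95% interval clears the null.** Let x be the smallest count whose Clopper-Pearson lower limit, the 0.025 quantile of Beta(x, n − x + 1), exceeds p0. In the same cohorts the lower limit is 0.0771 at 6, 0.0993 at 7 and 0.1228 at 8, so x = 8.

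**Step 3: probability of a discordant count.** This is P(c ≤ X < x). At p1 = 0.25 it is 0.1455 + 0.1662 = 0.312.

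| Cohort | n, p0, p1, alpha | Stated power | Exact power | c | x | Discordant at p1 | At p0 |
|---|---|---|---|---|---|---|---|
| HCC | 60, .20, .35, .10 | 88% | 89.0% | 17 | 19 | 14.2% | 5.5% |
| NSCLC failure | 80, .05, .15, .05 | 92% | 92.7% | 8 | 9 | 6.2% | 2.8% |
| Melanoma | 30, .05, .20, .10 | 87% | 87.7% | 4 | 5 | 13.3% | 4.5% |
| NSCLC second line | 30, .20, .40, .10 | 82% | 82.4% | 10 | 12 | 25.5% | 5.2% |
| Pancreatic, CRC, cervical (each) | 30, .10, .25, .10 | 79% | 79.7% | 6 | 8 | 31.2% | 6.5% |
| Ovarian, TNBC, esophageal, SCCHN (each) | 30, .15, .35, .10 | 87% | 87.6% | 8 | 10 | 23.4% | 6.0% |
| Glioblastoma | 30, .50, .80, .05 | 97% | 97.4% | 20 | 21 | 3.6% | 2.8% |

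All stated powers reproduce to within about one percentage point. A normal approximation does not fit (pancreatic group 84.4%, NSCLC second line 88.3%), so the design is the exact test.

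**Step 4: allow for how the cohorts are run.** NSCLC second line is powered on 30, but 40 are planned at 1200 mg. With n = 40, c = 12 and x = 14, and the discordance at p1 falls to 14.0%. In HCC the second 30 subjects enter only if more than 6 of the first 30 respond. Requiring that, and ignoring the difference between confirmed and unconfirmed response, gives 12.8% instead of 14.2%. In NSCLC failure the interim rule stops at 2 or fewer of 40 and pauses at 3 or 4. The figure becomes 5.3% if a pause always resumes and 2.2% if it never does. These rules are non-binding, so the adjusted figures are alternatives to the table, not replacements.

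**Step 5: ask what the plan decides with the interval.** In the readable text, nothing. Section 8.5.1 gives it an estimation role. The readable stopping rules in Section 8.6 use responder counts. Section 8.5.2.2 tabulates the number of responders, so the observed count can be set directly against c. Each c needs only the n, p0 and alpha that the protocol already states.

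**The case for a change.** The strongest case for a change is that discordant counts are not rare. If all 12 cohorts sat at their alternatives, the expected number landing on one is 0.142 + 0.062 + 0.133 + 0.255 + 3 × 0.312 + 4 × 0.234 + 0.036 ≈ 2.5; if all sat at their nulls it is about 0.6. The label of exploratory analysis does not say how a stated null, alpha and power should be read at the end. A remedy would also be cheap and exact: a two-sided 80% interval (90% for the two cohorts at one-sided 5%) first clears the null at exactly c in every cohort, for example 0.1086 at 6/30 against 10%, and 0.5006 at 20/30 against 50%.

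All of that arithmetic stands, and the extra interval would be a harmless courtesy to readers. It does not show that the plan is wrong. The discordance appears only when an estimation interval is used as a test, which the protocol does not ask for. The total of 2.5 takes every cohort at its alternative and NSCLC second line at 30; with 40 it is 2.5 − 0.25 + 0.14 ≈ 2.4. The supplied SAP does not settle the matter either way. Its Section 9.10 says no tests are performed and 95% intervals are descriptive, which agrees with the protocol, but that document covers only a cancelled addendum to the study report.

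**Conclusion.** No change is needed. The powers are correct at their stated alphas, and the 95% interval is a valid description of uncertainty that errs on the strict side, so it cannot inflate an efficacy claim. A cohort-size justification at one error rate beside a conventional 95% interval for reporting is ordinary practice in an exploratory single-arm expansion. It does mean that at one or two counts per cohort the two displays point in different directions. An analyst resolves this by comparing the tabulated responder count with the cutoff that the design fixes.

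The effect is on interpretation only, with the probabilities shown above. Power figures computed as if the 95% interval were the criterion should not be quoted, because no readable text makes it one.

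This rests on two assumptions. The first is that the redacted parts of Sections 8.1, 8.1.2 and 8.6 and the cohort analysis plans, which were not supplied, do not make the 95% interval a success rule. The second is that the descriptive and exploratory labels are meant as written. If those documents already give a final rule, the point disappears altogether.
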